4) Physical and Laboratory Test Findings

- a) Estimated glomerular filtration rate (eGFR) < 15 ml/min/1.73 m²
- b) Have persistent abnormal serum electrolytes not resolved between screening and start of the study drug infusion, as defined by any of the following:
 - i) A sodium (Na⁺) concentration < 130 or > 145 mEq/L (mmol/L)
 - ii) A potassium (K⁺) concentration < 3.2 or > 5.5 mEq/L (mmol/L)
- c) Have severe anemia, as documented by a hemoglobin < 9 g/dL (< 5.59 mmol/L)

5) Allergies and Adverse Drug Reaction

- a) Any history of allergic reaction to BMS-986231, or its components, Captisol® or potassium acetate.

- b) Allergic reactions to organic nitrates

6) Other Exclusion Criteria

- a) Prisoners or participants who are involuntarily incarcerated. (Note: under certain specific circumstances a person who has been imprisoned may be included or permitted to continue as a participant. Strict conditions apply and Bristol-Myers Squibb's approval is required.)
- b) Participants who are compulsorily detained for treatment of either a psychiatric or physical (e.g., infectious disease) illness
- c) Participation in an investigational clinical drug study within 30 days or 5 elimination half-lives, (whichever is longer) prior to randomization.
- d) Prior participation and treatment in a study using BMS-986231, CXL-1427, or CXL-1020
- e) Alcohol beverage consumption within 6 hours prior to randomization.
- f) Low quality echocardiographic visualization windows and image acquisition
- g) Body weight < 45 kg or ≥ 140 kg
- h) Known hypersensitivity or contra-indication to the intravenous echocardiography contrast agent, in the event contrast echocardiography is used

Eligibility criteria for this study have been carefully considered to ensure the safety of the study participants and that the results of the study can be used. It is imperative that participants fully meet all eligibility criteria.

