The following laboratory test result abnormalities should be captured on the non-serious AE CRF page or SAE Report Form electronic, as appropriate. Paper forms are only intended as a back-up option when the electronic system is not functioning.

- Any laboratory test result that is clinically significant or meets the definition of an SAE
- Any laboratory test result abnormality that required the participant to have study treatment discontinued or interrupted
- Any laboratory test result abnormality that required the participant to receive specific corrective therapy

It is expected that wherever possible, the clinical rather than laboratory term would be used by the reporting investigator (e.g., anemia versus low hemoglobin value).

9.2.7 *Potential Drug Induced Liver Injury (DILI)*

Wherever possible, timely confirmation of initial liver-related laboratory abnormalities should occur prior to the reporting of a potential DILI event. All occurrences of potential DILIs, meeting the defined criteria, must be reported as SAEs (see [Section 9.2](#) and [Appendix 3](#) for reporting details).

Potential drug induced liver injury is defined as:

- 1) AT (ALT or AST) elevation > 3 times upper limit of normal (ULN) if baseline values are within the normal range, or > 2 times the baseline values in case of baseline values above the upper limit of normal (ULN)

AND

2) Total bilirubin > 2 times ULN, without initial findings of cholestasis (elevated serum alkaline phosphatase),

AND

3) No other immediately apparent possible causes of AT elevation and hyperbilirubinemia, including, but not limited to, worsening heart failure, viral hepatitis, pre-existing chronic or acute liver disease, or the administration of other drug(s) herbal medications or substances known to be hepatotoxic.

9.2.8 *Other Safety Considerations*

Any significant worsening noted during interim or final physical examinations, electrocardiogram, x-ray filming, any other potential safety assessment required or not required by protocol should also be recorded as a non-serious or serious AE, as appropriate, and reported accordingly.

9.3 *Overdose*

An overdose is defined as the accidental or intentional administration of any dose of a product that is considered both excessive and medically important. All occurrences of overdose must be reported as an SAE (see [Section 9.2](#)).

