7.6.4 Clinical Laboratory Evaluations

The results of all protocol-specified clinical laboratory tests will be listed. Scheduled laboratory measurements will be summarized by treatment and scheduled time points for each laboratory test.

The criteria used for classifying laboratory test results as markedly abnormal will be listed.

Laboratory results for subjects with any marked laboratory abnormality (scheduled and unscheduled) will be listed. This listing will include all observations for the specific laboratory test and subject, not only the marked laboratory abnormalities. The frequency of subjects with any marked laboratory abnormality as well as hematology, serum chemistry, and urinalysis marked abnormalities, based on pre-specified criteria (see Table 6.6.2.4-1), will be presented.

Troponin T will be summarized descriptively by treatment for each time point, as well as change from baseline. Geometric mean and coefficient of variation (%CV) will also be presented for the original values and percent of baseline.

Table 6.6.2.4-1: Laboratory MA Criteria

Parameter	Test Code	Direction of Change	MA Criteria in US Standard Units (apply to labs collected after baseline only)	MA Criteria in SI Units (apply to labs collected after baseline only)
HEMATOLOGY				
Hemoglobin	HB	Low only	> 2 g/dl decrease compared to pre-dose or Value \leq 8 g/dl	> 20 g/l decrease compared to pre-dose or Value \leq 80 g/l
Hematocrit	HCT	Low only	< 0.75 \times pre-dose	< 0.75 \times pre-dose
Erythrocytes	RBC	Low only	< 0.75 \times pre-dose	< 0.75 \times pre-dose
Platelet Count	PLAT	Low Only	< 100,000/mm ³ (or < 100 \times 10 ⁹ cells/L)	< 100 \times 10 ⁹ cells/L
Leukocytes	WBC	Low/High	< 0.75 \times LLN or > 1.25 \times ULN, or if pre-dose < LLN then use < 0.8 \times pre-dose or > ULN if pre-dose > ULN then use > 1.2 \times pre-dose or < LLN	< 0.75 \times LLN or > 1.25 \times ULN, or if pre-dose < LLN then use < 0.8 \times pre-dose or > ULN if pre-dose > ULN then use > 1.2 \times pre-dose or < LLN
Neutrophils (absolute)	NEUTA	Low Only	< 1.0 \times 10 ³ cells/ μ L	< 1.0 \times 10 ⁹ cells/L
LIVER/KIDNEY				
Alkaline Phosphatase	ALP	High only	> 2 \times ULN	> 2 \times ULN
Aspartate	AST	High only	> 3 \times ULN, > 5 \times ULN, > 10 \times ULN	> 3 \times ULN, > 5 \times ULN, > 10 \times ULN

Table 6.6.2.4-1: Laboratory MA Criteria

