Parameter	Test Code	Direction of Change	MA Criteria in US Standard Units (apply to labs collected after baseline only)	MA Criteria in SI Units (apply to labs collected after baseline only)
Aminotransferase				
Alanine Aminotransferase	ALT	High only	$> 3 \times \text{ULN}$, $> 5 \times \text{ULN}$, $> 10 \times \text{ULN}$	$> 3 \times \text{ULN}$, $> 5 \times \text{ULN}$, $> 10 \times \text{ULN}$
Bilirubin, Total	TBILI	High only	$> 2 \times \text{ULN}$	$> 2 \times \text{ULN}$
Blood Urea Nitrogen	BUN	High only	$> 2 \times \text{ULN}$	$> 2 \times \text{ULN}$
Serum Creatinine	CREAT	High only	$> 1.5 \times \text{ULN}$	$> 1.5 \times \text{ULN}$
ELECTROLYTES				
Sodium, Serum	NA	Low/High	$< 0.95 \times \text{LLN}$ or $> 1.05 \times \text{ULN}$, or if pre-dose $< \text{LLN}$ then use $< 0.95 \times \text{pre-dose}$ or $> \text{ULN}$ if pre-dose $> \text{ULN}$ then use $> 1.05 \times \text{pre-dose}$ or $< \text{LLN}$	$< 0.95 \times \text{LLN}$ or $> 1.05 \times \text{ULN}$, or if pre-dose $< \text{LLN}$ then use $< 0.95 \times \text{pre-dose}$ or $> \text{ULN}$ if pre-dose $> \text{ULN}$ then use $> 1.05 \times \text{pre-dose}$ or $< \text{LLN}$
Potassium, Serum	K	Low/High	$< 0.9 \times \text{LLN}$ or $> 1.1 \times \text{ULN}$, or if pre-dose $< \text{LLN}$ then use $< 0.9 \times \text{pre-dose}$ or $> \text{ULN}$ if pre-dose $> \text{ULN}$ then use $> 1.1 \times \text{pre-dose}$ or $< \text{LLN}$	$< 0.9 \times \text{LLN}$ or $> 1.1 \times \text{ULN}$, or if pre-dose $< \text{LLN}$ then use $< 0.9 \times \text{pre-dose}$ or $> \text{ULN}$ if pre-dose $> \text{ULN}$ then use $> 1.1 \times \text{pre-dose}$ or $< \text{LLN}$
Chloride, Serum	CL	Low/High	$< 0.9 \times \text{LLN}$ OR $> 1.1 \times \text{ULN}$, or if pre-dose $< \text{LLN}$ then use $< 0.9 \times \text{pre-dose}$ or $> \text{ULN}$ if pre-dose $> \text{ULN}$ then use $> 1.1 \times \text{pre-dose}$ or $< \text{LLN}$	$< 0.9 \times \text{LLN}$ OR $> 1.1 \times \text{ULN}$, or if pre-dose $< \text{LLN}$ then use $< 0.9 \times \text{pre-dose}$ or $> \text{ULN}$ if pre-dose $> \text{ULN}$ then use $> 1.1 \times \text{pre-dose}$ or $< \text{LLN}$

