Calcium, Total	CA	Low/High	$< 0.8 \times \text{LLN}$ or $> 1.2 \times \text{ULN}$, or if pre-dose $< \text{LLN}$ then use $< 0.75 \times \text{pre-dose}$ or $> \text{ULN}$ if pre-dose $> \text{ULN}$ then use $> 1.25 \times \text{pre-dose}$ or $< \text{LLN}$	$< 0.8 \times \text{LLN}$ or $> 1.2 \times \text{ULN}$, or if pre-dose $< \text{LLN}$ then use $< 0.75 \times \text{pre-dose}$ or $> \text{ULN}$ if pre-dose $> \text{ULN}$ then use $> 1.25 \times \text{pre-dose}$ or $< \text{LLN}$
Bicarbonate	HCO3	Low/High	$< 0.75 \times \text{LLN}$ or $> 1.25 \times \text{ULN}$, or if pre-dose $< \text{LLN}$ then use $< 0.75 \times \text{pre-dose}$ or $> \text{ULN}$ if pre-dose $> \text{ULN}$ then use $> 1.25 \times \text{pre-dose}$ or $< \text{LLN}$	$< 0.75 \times \text{LLN}$ or $> 1.25 \times \text{ULN}$, or if pre-dose $< \text{LLN}$ then use $< 0.75 \times \text{pre-dose}$ or $> \text{ULN}$ if pre-dose $> \text{ULN}$ then use $> 1.25 \times \text{pre-dose}$ or $< \text{LLN}$
OTHER CHEMISTRY				
Creatine Kinase	CK	High only	$> 5 \times \text{ULN}$	$> 5 \times \text{ULN}$

Table 6.6.2.4-1: Laboratory MA Criteria

Parameter	Test Code	Direction of Change	MA Criteria in US Standard Units (apply to labs collected after baseline only)	MA Criteria in SI Units (apply to labs collected after baseline only)
Total Protein	TPRO	Low/High	< 0.9 × LLN or > 1.1 × ULN, or if pre-dose < LLN then use 0.9 × pre-dose or > ULN if pre-dose > ULN then use 1.1 × pre-dose or < LLN	< 0.9 × LLN or > 1.1 × ULN, or if pre-dose < LLN then use 0.9 × pre-dose or > ULN if pre-dose > ULN then use 1.1 × pre-dose or < LLN
Glucose, Serum Fasting	GLUCF	Low/High	< 0.8 × LLN or > 1.5 × ULN, or if pre-dose < LLN then use < 0.8 × pre-dose or > ULN if pre-dose > ULN then use > 2.0 × pre-dose or < LLN	< 0.8 × LLN or > 1.5 × ULN, or if pre-dose < LLN then use < 0.8 × pre-dose or > ULN if pre-dose > ULN then use > 2.0 × pre-dose or < LLN
Uric Acid	URIC	High only	> 1.5 × ULN, or if pre-dose > ULN then use > 2 × pre-dose	> 1.5 × ULN, or if pre-dose > ULN then use > 2 × pre-dose
Albumin		Low only	≤ 2 g/dL	≤ 20 g/L

URINALYSIS

Protein, Urine	UPRO	High only	If missing pre-dose then use ≥ 2, or if value ≥ 4, or if pre-dose = 0 or 0.5 then use ≥ 2, or if pre-dose = 1 then use ≥ 3, or if pre-dose = 2 or 3 then use ≥ 4	If missing pre-dose then use ≥ 2, or if value ≥ 4, or if pre-dose = 0 or 0.5 then use ≥ 2, or if pre-dose = 1 then use ≥ 3, or if pre-dose = 2 or 3 then use ≥ 4

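### The marked-abnormality rules for creatinine and BUN ignore the pre-dose value, so stable renal impairment is counted under each treatment and large rises from normal are not (minor)

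*SAP*

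**What the plan says.** SAP 7.6.4 states that "The frequency of subjects with any marked laboratory abnormality as well as hematology, serum chemistry, and urinalysis marked abnormalities, based on pre-specified criteria" will be presented, and points to Table 6.6.2.4-1. The column headings say that the criteria "apply to labs collected after baseline only".

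- **Serum creatinine:** more than 1.5 × ULN, no pre-dose clause.
- **BUN:** more than 2 × ULN, no pre-dose clause.
- **Uric acid**, in the same table: "> 1.5 × ULN, or if pre-dose > ULN then use > 2 × pre-dose".

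The only renal entry limit, in Protocol 6.2, excludes "Estimated glomerular filtration rate (eGFR) < 15 ml/min/1.73 m²". Neither creatinine nor BUN has a limit of its own.

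The sentence on frequencies does not name the grouping. I read it as by treatment, because SAP 7.6.4 summarises scheduled laboratory values by treatment and Protocol 10.3.2 says the same.

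**The concern.** In a crossover, a marked-abnormality table is informative when a flag reflects something that happened after the infusion started. A fixed multiple of ULN does not separate a new abnormality from one the subject brought into the trial. Heart-failure patients with eGFR down to 15 are eligible, so some may start each treatment day already above the creatinine or BUN cut-off.

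Two errors follow. A stably impaired subject is counted without any change in kidney function. A subject who starts in the normal range can have a large rise without being counted. Renal effect is a reasonable question for a vasodilating infusion: Protocol 9.3 names hypotension as the likely immediate effect of overdose, and Protocol 9.4.4 collects cystatin C and N-Gal. In the visible text of SAP 7.6.4, this frequency is the only subject-level incidence specified for renal laboratory values.

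**Working it through.** The plan gives no figure to reproduce. The check compares threshold rules, working in multiples of ULN because the documents give no reference ranges.

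**Step 1. Which rows use the pre-dose value (SAP Table 6.6.2.4-1).**
- With a pre-dose clause: haemoglobin, haematocrit, erythrocytes, leukocytes (4); sodium, potassium, chloride, calcium, bicarbonate (5); total protein, glucose, uric acid (3); the urinalysis rows (5). Total 4 + 5 + 3 + 5 = 17.
- Without: platelets, neutrophils, ALP, AST, ALT, bilirubin, BUN, creatinine, CK, albumin. Total 10.
- So 17 of 27 rows use it. Liver/kidney is the only block in which no row does.

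**Step 2. Can a stable, eligible subject be flagged?**
- Creatinine: yes, whenever the pre-dose value exceeds 1.5 × ULN. For example, a stable 1.8 × ULN is flagged because 1.8 > 1.5.
- BUN: yes, whenever the pre-dose value exceeds 2 × ULN.

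**Step 3. Effect on the table.** Let s subjects be stably above the cut-off and sampled after baseline under all three treatments. Let a and b be the numbers newly flagged on two treatments, each with n subjects.
- Frequencies: (s + a)/n and (s + b)/n. The ratio (s + a)/(s + b) is pulled towards 1 as s grows.
- The s subjects are already counted, so a further rise in one of them on one treatment adds nothing to the contrast.
- Each such subject adds 1/42 = 2.4 percentage points to each treatment at the randomised number, or 1/36 = 2.8 at the planned completers. The documents give no prevalence. Assuming s = 1, 2 or 4 with n = 42, the added frequency is 2.4, 4.8 or 9.5 points.

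**Step 4. Rise needed to be flagged (cut-off ÷ pre-dose value).**

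| Pre-dose (× ULN) | Creatinine, 1.5 ÷ pre-dose | BUN, 2 ÷ pre-dose |
|---|---|---|
| 0.5 | 3.0-fold | 4.0-fold |
| 0.8 | 1.9-fold | 2.5-fold |
| 1.0 | 1.5-fold | 2.0-fold |
| 1.2 | 1.25-fold | 1.7-fold |

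**Step 5. Does the same fault reach the liver tests?**
- AST/ALT: the lowest flag is above 3 × ULN. Protocol 6.2 excludes values above 3 × ULN, and Protocol 5.1 checks treatment-day transaminases against the entry limits. A stable eligible subject is not flagged.
- Bilirubin: the flag is above 2 × ULN and exclusion is above 3 mg/dL. With ULN assumed at 1.0, 1.2, 1.3 or 1.5 mg/dL, the window in which a stable eligible subject is flagged is 1.0, 0.6, 0.4 or 0 mg/dL wide.
- Against Protocol 9.2.7, whose transaminase limb begins "AT (ALT or AST) elevation > 3 times upper limit of normal (ULN) if baseline values are within the normal range" and switches to twice baseline when baseline is above ULN: the cut-offs agree for a normal baseline and at 1.5 × ULN. They differ at 1.2 × ULN (2.4 against 3.0) and at 2.0 × ULN (4.0 against 3.0). The bilirubin cut-off is 2 × ULN in both.

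**The case against.** The strongest reply is that this is a descriptive screen, not the only view of the data. All laboratory results are listed and summarised by treatment and time point. A flagged subject's listing shows every value of that test, so a stable abnormality is recognisable. SAP 8.3 has conventions for change-from-baseline and shift tabulations, and Protocol 9.2.6 makes clinically significant results reportable as adverse events. A stably flagged completer counts equally under each treatment, so no treatment gains. All of that stands and is why the point is minor. It does not close the gap: SAP 7.6.4 commits to change from baseline only for troponin T, and an unflagged doubling of creatinine would appear only in the full listing.

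A reader might infer more than the documents support:

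- **That the AST/ALT and bilirubin rules share the fault.** Step 5 shows that stable AST/ALT subjects are not flagged and that the bilirubin window is narrow or absent.
- **That the SAP contradicts the protocol's liver-injury rule.** Protocol 9.2.7 is a composite trigger for reporting an SAE: transaminases, bilirubin and no other apparent cause. The SAP table tabulates single analytes. They differ only for transaminases with baseline above ULN, and different purposes allow that.
- **That acute renal rises would be missed by the trial.** They may be missed by this count, not by the listings, summaries or adverse-event reporting.
- **That stable subjects are certain to be flagged in all three periods.** Table 2-2 gives no draw time for the central laboratory, and the local tests are taken before the infusion. The number of post-baseline samples per period cannot be confirmed.
- **That local and central values are mispaired in the present flags.** The creatinine and BUN rules use no pre-dose value, and for marked abnormalities SAP 8.3 takes the worst value, not the closest day.

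**Conclusion.** The point holds for creatinine and BUN only. Their rules flag stable renal impairment that the entry criteria allow, adding the same non-treatment count (about 2.4 points per such subject) to each treatment with a post-baseline sample. They also require a rise of more than 3-fold (creatinine) or 4-fold (BUN) from 0.5 × ULN. The result is dilution, not bias towards a treatment. How many subjects are affected is unknown.

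The conclusion assumes that the frequency is presented by treatment and that post-infusion samples exist. Severity is minor: the primary analysis, sample size and error rate are untouched.

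**What to change.** In SAP Table 6.6.2.4-1, keep the creatinine and BUN rows for reference and add a treatment-emergent row for each, evaluated by period. Count a subject under a treatment if either condition is met, and show the two separately:

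1. The post-baseline value exceeds the existing ULN cut-off and that period's pre-dose value did not.
2. The post-baseline value exceeds a pre-specified multiple of that period's pre-dose value, for example 1.5. Separate display matters because this can occur within the normal range: 0.6 to 0.95 mg/dL is 0.95/0.6 = 1.58-fold.

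Copying the uric-acid clause ("or if pre-dose > ULN then use > 2 × pre-dose") would not be enough. It would stop flagging a stable creatinine of 1.8 × ULN, since the cut-off becomes 3.6 × ULN, but from 0.5 × ULN a rise above 3-fold would still be needed.

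Take both values from the central laboratory, since Protocol 9.4.4 has creatinine and BUN measured locally as well. Confirm that central samples are drawn before and after each infusion. SAP 8.2 does not impute missing baselines, so use as denominator the subjects with both values in the period.

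Leave the AST/ALT and bilirubin cut-offs unchanged. Substituting the Protocol 9.2.7 limits would remove the flag from an ALT rise of 2.0 to 3.9 × ULN, which is counted now.

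The cost is a few table rows, a little derivation code and a small departure from the existing criteria table. Trial conduct does not change if the central samples are already drawn.

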7.6.5 ECG

All recorded ECGs (heart rate (HR), QT (QT, Bazett's corrected QT [QTcB], Fridericia's corrected QT [QTcF]), PR and QRS intervals) will be listed.

Summaries of ECG parameters (heart rate (HR), QT (QT, QTcF), PR and QRS intervals) will be tabulated by time point and treatment. Summaries of ECG parameters will include change from baseline at list of time points.

If QTcF is not available in the database, QTcF will be calculated using the reported uncorrected QT Interval and Heart Rate, and the following formula:

$$QTcF = \frac{QT}{(60/HEART\ RATE)^{1/3}}$$

Subjects with ECG intervals outside of a pre-specified range will also be listed.

The following criteria will be used to determine ECG results that are outside of a pre-specified range:

PR (msec):	Value > 200
QRS (msec):	Value > 120
QT (msec):	Value > 500 or change from baseline > 30
QTcF (msec):	Value > 450 or change from baseline > 30

7.6.6 Vital Signs

Vital sign measurements will be summarized by treatment group at each scheduled time point using descriptive statistics.

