2 SCHEDULE OF ACTIVITIES

Table 2-1: Time & Event Schedule CV013020, Screening Period

Procedure	Screening Visit	Notes
Eligibility Assessments		
Informed Consent	x	A participant is considered enrolled only when a protocol specific informed consent is signed.
Inclusion/Exclusion Criteria	x	
Medical History	x	
Concomitant medications	x	
Echocardiography eligibility assessment	x	As described in the echocardiographic core lab manual, evaluation of image quality and assessment of ejection fraction
Safety Assessments		
Physical Examination	x	If the screening physical examination is performed within 3 days prior to first dosing then a single exam may count as both the screening and pre-dose evaluation. Includes height and weight.
Vital Signs	x	Includes body temperature, respiratory rate, and seated blood pressure and heart rate. Blood pressure and heart rate should be measured after the participant has been resting quietly for at least 5 minutes.
Adverse Events Assessment	x	SAEs must be collected from the date of the participant's Informed consent.
Local Laboratory Tests	x	Hematology, Serum chemistry, NT-proBNP or BNP (details in the protocol section 9.4.4)
Pregnancy Test (WOCBP only)	x	

Table 2-2: Time & Event Schedule CV013020, Treatment and Follow-up Study Periods

Procedure	Treatment Period					Notes
	Period 1 Day 1	Washout 5-28 Days	Period 2 Day 1	Washout 5-28 Days	Period 3 Day 1	
Safety Assessments						Washout between periods should be at least 5 days and no more than 4 weeks.
Weight	x		x		x	Weight pre-and end of the infusion in each treatment period.
Targeted physical examination	x		x		x	Based on subject's report since the screening visit. Includes temperature, signs and symptoms of congestion.
Vital Signs (Blood pressure and heart rate)	x		x		x	Prior to infusion. 30 minutes at first hour, then every 1 hour until discontinuation of infusion, then at 1 hour, 2 hour and 3.5 hour after end of infusion in each treatment period.
Peripheral Oxygen Saturation	x		x		x	Prior and end of the infusion in each treatment period, measured with a pulse oximeter device.
12 lead ECG	x		x		x	Prior to the infusion and after end of infusion in each treatment period.
Urinary output	x		x		x	From start of infusion to 3 hours after end of infusion in each treatment period.
Telemetry	x		x		x	From start of infusion to 3 hours after end of infusion in each treatment period.

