The administration of the study drugs will be done through an infusion pump connected to a single peripheral IV line. After priming the infusion set tubing and connecting the lines to the intravenous catheter, the pump should be set to deliver the rates of infusion indicated on the infusion bag label according to the up-titration schedule (See [Section 5.1](#)).

The pump infusion volume display should be re-set to 0 after priming the infusion line and just prior to the start of the infusion, and the total volume infused at the conclusion of the infusion after 5-hours, or at the time of any early discontinuation, should be recorded in the clinic source documents.

[figure not shown]
At any time during the administration of study drug, the study drug infusion must be discontinued if an adverse event or any other safety issue suggests it is not in the patient's best interest to continue to receive study drug.

The investigator has the option to adjust the study drug dosage level downward by 50%, interrupt or discontinue the study drug infusion in patients that develop hypotension, or if the patient experiences symptomatic hypotension that is not easily tolerated, as follows (and shown in Figure 7.4-1)

- **Study drug reduction:** Study drug is decreased by 50% if SBP decreases to levels <90 mmHg but ≥ 80 mmHg. The dose cannot be subsequently increased.
- **Study drug interruption:** Study drug is interrupted for 1 hour if SBP decreases to <80 mmHg or symptoms of low blood pressure occur within the first 4 hours of infusion. If the SBP is ≥ 105 mmHg after one hour interruption, the study drug could be resumed at 50 % of the dose to complete 5-hours of effective study drug infusion.
- **Study drug discontinuation:** Study drug will be permanently discontinued if SBP remains < 105 mmHg after 1 hour interruption or if SBP decreases to levels <80 mmHg or symptoms of low blood pressure occur after 4 hours of infusion.

End of infusion procedures should be done as soon as possible after interruption or discontinuation of the study drug. If an infusion in a given period is discontinued, patients remain eligible to complete subsequent periods.

Figure 7.4-1: BP Management Algorithm

Any decision to lower the dosage level of study drug or discontinue study drug should be based on the investigator's assessment of the patient's overall clinical stability, in the context of appropriate ongoing monitoring of the patient's condition.

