10.3.2 Safety Analyses

All safety analyses will be performed on the Safety Population (see [Section 10.2](#)).

For safety analyses, all recorded adverse events for each period will be listed and tabulated by system organ class, preferred term and treatment. Vital signs and clinical laboratory test results will be listed and summarized by treatment. Any significant physical examination findings, and clinical laboratory results will be listed. ECG readings will be evaluated by the investigator and abnormalities, if present, will be listed.

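### SAP 7.6.6 summarises blood pressure only at scheduled times, so subjects stopped for hypotension drop out of the later on-infusion summaries and no output counts who crossed 90 or 80 mmHg

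*SAP*

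**What the plan says.** - **Analysis.** The whole of SAP 7.6.6 is: "Vital sign measurements will be summarized by treatment group at each scheduled time point using descriptive statistics". SAP 7.1 defines descriptive statistics for continuous variables as N, mean, SD, median, minimum and maximum. Protocol 10.3.2 asks for more: "Vital signs and clinical laboratory test results will be listed and summarized by treatment". SAP 7.6.6 does not repeat the listing.
- **Collection.** Protocol Table 2-2 takes blood pressure before the infusion, then "30 minutes at first hour, then every 1 hour until discontinuation of infusion", and again at 1, 2 and 3.5 hours after the infusion ends.
- **Algorithm.** Protocol 7.4 has three steps. First, "Study drug is decreased by 50% if SBP decreases to levels <90 mmHg but ≥ 80 mmHg". Second, in the first 4 hours, "Study drug is interrupted for 1 hour if SBP decreases to <80 mmHg or symptoms of low blood pressure occur"; the infusion may resume at half dose if SBP is at least 105 mmHg an hour later. Third, it is stopped permanently if SBP is still below 105 mmHg after that hour, or if SBP below 80 mmHg or symptoms occur after 4 hours.
- **Several readings.** SAP 8.3 keeps the reading nearest the planned time when more than one falls in the same hour range. Its separate rule for vital signs chooses by day, so it cannot choose among readings taken on one treatment day.
- **Comparison with other safety data.** Laboratory values get abnormality criteria, unscheduled results and a worst-value rule (SAP 7.6.4, 8.3). ECGs get out-of-range limits and change from baseline (7.6.5). Oxygen saturation gets change from baseline (7.6.9). SAP 7.6.6 gives blood pressure none of these.

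**The concern.** SBP is the variable that drives the dosing algorithm, yet its planned summary has no threshold, no per-subject minimum and no rule for a stopped infusion. Leaving the hourly series depends partly on SBP itself, so the later on-infusion values come from a group selected on the outcome.

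In a crossover the comparison is affected as well. Protocol 7.4 lets a subject stopped in one period complete the others. That subject can be missing at hours 4 and 5 on an active drug but present at those hours on placebo. The two column means then describe different people, and the apparent gap tends to shrink most for the treatment that causes most hypotension. A report could show a modest mean difference without stating how many subjects crossed the trial's own action limits.

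**Working it through.** The plan states no figure for these summaries, so there is none to reproduce. The check has three parts.

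**1. Who leaves the hourly series (Protocol 7.4 against Table 2-2)**

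| Course | Infusion | Later hourly readings |
|---|---|---|
| SBP 80 to <90 | continues at half dose | continue |
| SBP <80 or symptoms in first 4 h, SBP ≥105 after 1 h, resumed | resumes at half dose | continue |
| Same trigger, SBP <105 after 1 h | stopped | end; move to 1, 2 and 3.5 h after infusion |
| SBP <80 or symptoms after 4 h | stopped | end; at most the hour-5 value is lost |

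Example: SBP falls below 80 at hour 2 and the infusion is interrupted. At hour 3 SBP is below 105 and the infusion is stopped. Hours 4 and 5 are lost. Any hour-3 reading is off drug, but nothing in SAP 7.6.6 or 8.3 separates it from on-drug readings. The later reading labelled 1 hour after infusion is pooled with readings from subjects who had the full 5 hours.

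**2. What the planned outputs can show**

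- *N and minimum per time point (SAP 7.1).* A minimum below 80 mmHg at hours 1, 2 and 3 is compatible with one subject low three times, three different subjects, or more. The count cannot be recovered. N does not separate infusing from interrupted subjects.
- *SAP 8.3.* If a low reading prompts a re-check and a routine reading in the same hour range lies nearer the planned time, the low reading is left out of the summary. If the low reading is the only or the nearest one, it enters.
- *Dose-change counts (SAP 7.4).* These count actions. Adjustment is at the investigator's discretion, and symptoms or other adverse events also lead to it, so actions and SBP crossings need not agree.
- *Adverse-event tables (SAP 7.6.3).* These depend on what the investigator reports and carry no SBP values.

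**3. Direction and illustrative size**

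Let k of n subjects have left, and let their SBP, had they stayed on drug, be g mmHg below the mean M of those remaining. The full-group mean is M − (k/n)g, so the observed mean exceeds it by (k/n)g. The only input from the documents is n = 42, the randomisation target. k and g are assumptions.

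| k of 42 | g = 20 | g = 30 | g = 40 |
|---|---|---|---|
| 2 | 1.0 | 1.4 | 1.9 |
| 4 | 1.9 | 2.9 | 3.8 |
| 8 | 3.8 | 5.7 | 7.6 |

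For example, 4/42 × 30 = 2.9 mmHg.

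A simulation gave the same direction in every scenario. Its assumed inputs were: baseline SBP Normal(125, 12) truncated at the 110 mmHg entry limit, mean fall 10 to 25 mmHg with between-subject SD 8, within-subject SD 6 to 9, and checks every 15 minutes. The hour-5 excess was 0.3 to 5.6 mmHg. It removed every subject at the first value below 80 and modelled neither resumption nor dose halving. It therefore overstates loss and does not follow the protocol's pathway; only its direction is used here.

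**The case against.** A reader might infer that the readings that trigger a dose change need never be reported, or that the most hypotensive subjects all vanish from the data. The documents support neither:

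- Protocol 10.3.2 requires vital signs to be listed, and silence in the SAP does not cancel that.
- SBP below 80 mmHg in the first 4 hours leads first to an interruption, and 80 to <90 mmHg to a halved dose. Subjects with a reduced dose or a resumed infusion stay in the series, and stopped subjects are still measured afterwards.
- A low value at a scheduled time enters that time point's mean and bounds its displayed minimum.
- Interruptions, reductions and discontinuations are counted by treatment, as are adverse events. Protocol Appendix 3 makes clinically significant vital-sign abnormalities adverse events.

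So frequent hypotension would be expected to show somewhere in the report.

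Two further objections are fair. The bias is measured against the mean that would have been seen had stopped subjects kept infusing, which a descriptive safety table does not claim to estimate. Also, SAP 7.7 and some exploratory endpoints are not in the public text, and table layouts are left to a separate Data Presentation Plan (SAP 9), so extra blood-pressure outputs cannot be excluded.

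These points limit the concern to the summary tables and to the visible text. They do not supply a count of subjects below 90 or 80 mmHg, a per-subject minimum, or a rule for off-drug readings.

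**Conclusion.** The concern holds in a limited form. Summaries at scheduled times lose subjects permanently stopped for hypotension, which tends to raise the later on-infusion SBP means. They mix post-infusion values that follow different exposures, and they can omit off-schedule low readings. The other planned outputs show part of the signal, but none states how many subjects crossed 90 or 80 mmHg.

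The direction rests on one assumption: that stopped subjects would have had lower on-drug SBP than those who continued. The size is unknown, because the documents give no on-drug SBP distribution and no stopping rate. The 1.0 to 7.6 mmHg in the table shows how the mean responds to assumed losses and is not an estimate for this trial. It would be wrong to read it as showing that the plan hides hypotension. This is a low-cost improvement to the safety tables and does not affect the primary analysis.

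**What to change.** In SAP 7.6.6, by treatment:

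1. Summarise each subject's minimum SBP and largest fall from period baseline, from infusion start to 3.5 hours after its end, using all recorded scheduled and unscheduled readings.
2. Give the number and percent of subjects with SBP <90 and <80 mmHg in that window.
3. At each scheduled time show the number still infusing, and flag readings taken while the drug was interrupted or stopped.
4. Carry over the vital-sign listing required by Protocol 10.3.2.

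The cost is about two extra tables, the added column and flag, and one listing the protocol already requires. No new measurement is needed if unscheduled blood-pressure readings are captured in the CRF; the documents do not say so, and this should be confirmed. The drawback is that a minimum depends somewhat on how often pressure is re-checked, so the number of readings per subject should be shown beside it. No dosing rule changes.
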